Participants were randomized 1:1 to the consumer health informatics smartphone-based intervention app or a control app with only data collection. Permuted block randomization (pairs) was performed using a computer-generated code within a secure central online data management system, Research Electronic Data Capture (REDCap), which was used to store and manage all participant data. No randomization was instituted for the clinician-facing intervention; instead, the decision support tool was embedded into the electronic health record to facilitate optimized opioid prescription upon discharge based on recorded inpatient use. This was implemented after half of the participants were enrolled. The principal investigator, coinvestigators, clinical coordinating center staff, participants, and statisticians remained masked to treatment assignment until the database was locked for analysis.

Sample Size Justification

To estimate power and sample size for the primary outcome, self-reported cumulative opioid use in the four weeks after discharge, investigators combined data from previous observational studies on opiates taken at one week from discharge, where variability in opioid consumption is greatest, and summed across four weeks from discharge and then log-transformed values appropriately. Investigators utilized SAS Proc Power (version 15.2, SAS Institute Inc., Cary, NC, USA) software and specified significance level alpha = 0.05 two-tailed. Across decision support tool activation status and surgical subspecialties, 300 participants per app group provided 85% power to detect minimum effect sizes (ES) of 0.23 in opioids consumed at one week and of 0.245 in opioids consumed across four weeks. Data was similarly

combined for pain intensity scores from prior studies and could detect a minimum effect size of 0.244 in pain intensity t-score at week one following discharge. Within decision support tool type and across specialty (i.e., the three-way interaction among app, decision support tool, and time), 150 participants per group provided 85% power to detect minimum effect sizes of 0.35 in opioids consumed at one week, 0.35 in opioids consumed across four weeks, and 0.35 in pain intensity t-score at one week after discharge.

Procedures

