For the primary analysis, the effect of the intervention app on self-reported cumulative opioid use in the four weeks after discharge was modeled by log-transforming the outcome variable and then fitting a linear regression model with the app treatment group as the covariate. The treatment effects were estimated as ratio of geometric means. A sensitivity analysis was conducted using quantile regression to test the robustness of results to outliers. A model was fit with an interaction between app and decision support tool groups to evaluate potential multiplicative effects between the groups. Analysis was on a modified intention-to-treat basis, excluding participants that did not engage with the intervention or answer survey questions. There were no partial responses to the opioid-related outcomes. Missing data from pain-related survey responses were imputed from the mixed effects model.

For the secondary analysis, the effect of the intervention app on opioids prescribed at discharge was modeled by log-transforming the outcome and fitting a linear regression model with the app treatment group as the covariate. The effect of the intervention app on supplementary opioid requirements in the four weeks after discharge, opioid disposal, and non- opioid prescriptions in the four weeks after discharge was evaluated using a logistic regression model. The effect of the app on pain intensity and interference t-scores was evaluated by fitting linear mixed models with fixed covariates for app treatment group and time (categorical), and random effects for participant identification code. No interim analyses were planned because the population studied was not considered high risk for adverse events, the interventions were generally considered not harmful and to prevent alpha dilution.

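### The primary app model omits the tool period that the trial itself creates, which costs some precision, and the plan does not commit to reporting the app ratio in each period

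*Combined protocol and SAP*

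**What the plan says.** Under Statistical analysis, the primary analysis of four-week opioid use is on the log scale, "fitting a linear regression model with the app treatment group as the covariate". The effect is expressed as a ratio of geometric means. No other term appears in the primary model. The same paragraph adds: "A model was fit with an interaction between app and decision support tool groups to evaluate potential multiplicative effects between the groups".

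Randomization and masking explains where the second factor comes from. The app is randomised 1:1 in permuted blocks of two. The decision support tool is not randomised: "This was implemented after half of the participants were enrolled". Procedures limits the tool to second-half participants who needed no opioids in the 24 hours before discharge.

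Sample Size Justification states power for the pooled comparison: "Across decision support tool activation status and surgical subspecialties, 300 participants per app group provided 85% power". For the primary outcome the minimum effect is "of 0.245 in opioids consumed across four weeks". It also gives a within-tool figure: "150 participants per group provided 85% power to detect minimum effect sizes of 0.35 in opioids consumed at one week", with the same 0.35 for the four-week outcome.

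The plan does not say that the app ratio will be reported for each period, or how the pooled ratio would be read if the two differ.

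**The concern.** The tool is meant to change discharge prescribing, so average intake may differ between the two halves of the trial. This is a known, planned design factor, yet it is absent from the primary model. Two things follow, and they should be kept apart.

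1. **Precision.** Any difference in level between the halves goes into the residual variance and widens the interval for the app ratio.
2. **Interpretation.** The pooled ratio is a roughly equal-weight average, on the log scale, of the app effect without the tool and with it. The weights are set by when the tool was switched on. A hospital without such a tool would want the first; a hospital with one would want the second. If the two differ, the pooled figure describes neither, and the reader would have only the interaction test as a guide.

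**Working it through.** **Inputs from Sample Size Justification and Randomization and masking:** two-sided alpha 0.05; 300 per app group; 150 per app group in each period; effect 0.245 SD (pooled, four weeks) and 0.35 SD (within tool status); 1:1 allocation in pairs; tool on at half enrolment. **Assumptions:** effect sizes are standardised mean differences on the log scale; no exclusions; equal halves. The period shift and the period-specific app effects are not in the documents and are shown as ranges.

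**1. The plan's own figures.** Power = Φ(d·√(n/2) − 1.96).
- Pooled: 0.245 × √150 = 3.001; Φ(1.041) = 85.1%. The stated 85% is reproduced.
- Within period: 0.35 × √75 = 3.031; Φ(1.071) = 85.8%. The stated 85% is reproduced, as a simple two-group contrast within one period.

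**2. Bias from omitting the period.** In 2,000 simulated trials of 600 participants in pair blocks, with a 0.5 SD period shift, the app estimate averaged −0.241 with and without the period term. The largest difference in any trial was about 1e-15. There is no bias.

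**3. Precision lost by omitting the period.** A shift of s SD between equal halves multiplies the residual variance by 1 + s²/4. Power without the term is Φ(3.001/√(1 + s²/4) − 1.96).

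| Assumed shift s | Variance factor | Power without term | Power with term |
|---|---|---|---|
| 0.2 | 1.0100 | 84.8% | 85.1% |
| 0.5 | 1.0625 | 82.9% | 85.1% |
| 0.8 | 1.1600 | 79.6% | 85.1% |

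This formula is slightly pessimistic. Under exact pair balance only the reported standard error is inflated, because the estimate itself carries no period noise. Power is then Φ(3.001 − 1.96·√(1 + s²/4)), which gives 84.9%, 83.7% and 81.3%. Either way the loss is negligible to modest.

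**4. What pooling does if the app effects differ.** With equal halves the pooled effect is (d_off + d_on)/2. The interaction contrast has SE √(4/150) = 0.163 SD. As an illustration, set the tool-off effect to 0.245 SD.

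| d_on as share of d_off | Pooled effect | Pooled power | Difference between periods | Interaction power |
|---|---|---|---|---|
| 75% | 0.214 | 75% | 0.061 | 7% |
| 50% | 0.184 | 61% | 0.1225 | 12% |
| 0% | 0.123 | 32% | 0.245 | 32% |

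If the app effect vanishes only in a share f of second-half participants, the pooled effect is (1 − f/2) of the tool-off effect: 87.5%, 75% or 62.5% for f = 0.25, 0.5 or 0.75.

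**5. What the interaction test can detect.** For 85% power the two app effects must differ by (1.960 + 1.036) × 0.163 = 0.49 SD. At a difference of 0.35 SD, power is Φ(0.35/0.163 − 1.96), about 57%. Sample Size Justification describes its 150-per-group figure as an interaction, but its 85% at 0.35 SD is the power of the within-period contrast in step 1, not of a difference between periods.

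**6. Width of the within-period intervals.** 95% half-width 1.96 × √(2/150) = 0.23 SD, against 1.96 × √(2/300) = 0.16 SD pooled.

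**The case against.** The pooled contrast is a legitimate at-the-margins factorial estimand, and Sample Size Justification openly declares that it is taken across tool status. Low power for interaction is usual in factorial trials. Both points stand, and so the pooled ratio should remain primary.

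Several stronger readings are tempting, and the documents do not support them:

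- **That the missing term distorts the app ratio.** Pair-block allocation rules this out (step 2). Only a difference in the app effect between periods moves the pooled ratio away from the tool-off ratio, and a main effect for period does not change that. Modified intention-to-treat exclusions could upset the balance somewhat; their number is not given.
- **That the plan has no within-period estimate.** The planned interaction model yields an app ratio for each period, and within-tool power is given. Only the commitment to report the ratios is missing.
- **That a weaker app effect in the second half is built in, because less supply leaves less to reduce.** That argument applies to absolute intake. The effect here is a ratio, and a lower level does not by itself shrink a proportional reduction. Procedures also confines the tool to participants not needing opioids shortly before discharge, and reports that such intake was the strongest available predictor of later intake. They may take little with or without the tool. The direction is unknown: if the app works better alongside the tool, the pooled ratio overstates the tool-off effect.
- **That the 85% is wrong.** It is stated for a pooled effect of 0.245 SD and is correct for that. The table in step 4 gives 0.245 to the tool-off half as an illustration; the plan makes no such claim.

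**Conclusion.** The concern holds on two limited points.

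First, a known design factor is missing from the primary model. The cost is precision, not validity: from a fraction of a percentage point of power at a 0.2 SD period shift to about 4 to 5.5 points at 0.8 SD. The true shift is not in the documents.

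Second, the pooled ratio may under- or overstate the app effect in either period, and the interaction test is too weak to reassure. Even if the app effect fell from 0.245 SD to zero, the test would miss it about two times in three. A non-significant interaction would therefore say little about whether the pooled ratio represents both periods. Whether the effects do differ, and in which direction, cannot be told from the documents.

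A reader might also infer that a null pooled result should count as no app effect only if the tool-off interval excludes a relevant effect. That does not follow. The plan defines no margin of relevance, and such a rule would make an underpowered half-sample decisive: with 150 per group, power at 0.245 SD is only Φ(0.245 × √75 − 1.96) = 56%.

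**What to change.** Keep the pooled app ratio as the primary estimate and make two changes to Statistical analysis:

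1. Add tool period (off/on) to the primary model as a main effect. Define it by date relative to activation of the tool, not by whether the tool applied to a given participant, because that depends on opioid use after enrolment.
2. State that the app's ratio of geometric means, with its 95% CI, will be reported for the tool-off and tool-on periods from the planned interaction model, whatever the interaction p-value, and label both as supportive. Each is a randomised comparison, since the app was allocated 1:1 in pairs throughout.

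The cost is one degree of freedom, a few lines of text and two contrasts from a model already planned; no new data are needed. The downside is that the within-period intervals are about 1.4 times as wide as the pooled one (0.23/0.16), so neither should carry the conclusion alone. The 85% power statement for the pooled four-week contrast needs no change on this account.

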Investigators primarily tested a participant-facing app to reduce opioid intake which was designed and implemented through a user-centered design approach. The intervention app provided education on elements of pain management that could be modified by patients, including: 1) post-operative pain expectations, 2) pharmacologic alternatives to opioids, 3) opioid safety and appropriate disposal, and 4) non-pharmacological therapy, such as meditation. The control app featured the same interface but only collected patient data. The app was deployed to research team members and pilot participants for beta testing before finalization.

Baseline information was obtained from the participant in-person during the index hospitalization. During this visit, patients familiarized themselves with the format, asked questions, and received explanations regarding the apps' functionality. Following discharge, a weekly notification was sent to the participant, reminding them to complete standardized surveys and custom questionnaires during the first four weeks following discharge, a time when most opioids are consumed and when patients have shown to report consumption accurately. The day of discharge was considered day 0. If no responses were obtained via the app, participants were followed up by telephone.

In addition to the participant-facing app intervention, a clinician-facing decision support tool was operationalized for the second half of the study period for participants not requiring opioids 24 hours prior to discharge. Previous work in three diverse samples of surgical procedures found that among available predictor variables that could be incorporated into an electronic decision support tool, 24-hour pre-discharge opioid intake was most strongly associated with patient-reported post-discharge opioid intake.

Outcomes

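### The primary analysis excludes randomised participants for non-engagement or non-response after randomisation, and no planned analysis covers them, so the app comparison can be biased in either direction

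*Combined protocol and SAP*

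**What the plan says.** The analysis set is defined in one sentence of the Statistical analysis section: "Analysis was on a modified intention-to-treat basis, excluding participants that did not engage with the intervention or answer survey questions". The same paragraph adds "There were no partial responses to the opioid-related outcomes" and "Missing data from pain-related survey responses were imputed from the mixed effects model". The only sensitivity analysis named for the primary outcome is this: "A sensitivity analysis was conducted using quantile regression to test the robustness of results to outliers". The primary model regresses log four-week opioid use on app group alone.

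Other sections bear on the point:

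- **Outcomes:** the primary outcome is self-reported, so it exists only for people who answer.
- **Procedures:** on the comparator, "The control app featured the same interface but only collected patient data". On non-response, "If no responses were obtained via the app, participants were followed up by telephone".
- **Randomization and masking:** allocation is 1:1, and the masked groups include "participants, and statisticians remained masked to treatment assignment until the database was locked for analysis".
- **Sample Size Justification:** 300 per app group, 85% power, two-sided alpha 0.05, with a minimum effect size of 0.245 for opioids over four weeks.
- **Study design and participants:** re-hospitalization within 30 days is listed as an exclusion. Outcomes counts re-hospitalization as a serious adverse event.

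**The concern.** Randomisation makes the two groups comparable as assigned. Using an app and answering surveys after discharge can both depend on which app was assigned and on how the participant is recovering. Someone with little pain may ignore the app, and so may someone with severe pain. If the people removed differ from those kept, and do so differently by arm, part of the estimated app effect reflects who was removed. That could produce an apparent opioid reduction or hide a real one, and the primary model has no baseline covariates that might absorb some of it.

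The criterion is also unclear. Engagement has no definition. Read literally, engaging with the intervention might be a test that only one arm can fail, since the control app has no educational content.

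The re-hospitalization exclusion raises a related question, because its timing is not given. If it covers events after randomisation, it is a further exclusion of the same kind, and it touches events that the trial also counts as serious adverse events.

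**Working it through.** **1. What the exclusion sentence can mean**

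- *Reading A: failing either criterion excludes.* A participant who ignored the app but reported opioid use by telephone could be dropped despite having a primary outcome.
- *Reading B: only failing both excludes.* Telephone responders stay, but people with no opioid report are still left out, so the analysis is complete-case.

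The absence of partial responses does not mean the absence of missing data. It means each person has the whole opioid outcome or none of it.

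**2. Whether any planned analysis covers those excluded**

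- Quantile regression uses the same retained participants.
- Imputation is confined to pain scores.
- The app-by-tool interaction model and the baseline balance check do not restore anyone.
- No weighting, imputation of opioid use or full intention-to-treat analysis is described.

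On either reading, nothing does.

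**3. Reproducing the plan's figure**

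n per arm = 2(1.960 + 1.036)² / 0.245² = 299.2, rounded up to 300. A two-sample t test with 300 per arm has 85.0% power at 0.245. The four-week figure reproduces.

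**4. Bias from exclusion**

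Let p be the share excluded in an arm and d the mean of the excluded minus the mean of the retained, in SD of log opioid use. All values of p and d below are assumptions. The retained SD is taken as 1.

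- Bias (app minus control) = −(p_app × d_app − p_control × d_control). Negative values favour the app.
- SE = √[1/(300(1 − p_app)) + 1/(300(1 − p_control))].
- Type I error = P(|Z + bias/SE| > 1.96) when the true effect is zero.

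For 15% against 5% with d = 0.5 in both arms:

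- Bias = −(0.075 − 0.025) = −0.05.
- SE = √(1/255 + 1/285) = 0.0862.
- The ratio is 0.58 in absolute value, which gives 8.9%.
- 0.05/0.245 = 20% of the design effect.

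| Excluded, app / control | d, app / control | Bias (SD) | Type I error |
|---|---|---|---|
| 15% / 5% | +0.5 / +0.5 | −0.05 | 8.9% |
| 15% / 5% | −0.5 / −0.5 | +0.05 | 8.9% |
| 5% / 15% | +0.5 / +0.5 | +0.05 | 8.9% |
| 15% / 5% | +0.3 / +0.3 | −0.03 | 6.4% |
| 10% / 10% | +0.5 / +0.5 | 0 | 5.0% |
| 10% / 10% | +0.5 / 0 | −0.05 | 8.9% |
| 20% / 10% | +0.5 / 0 | −0.10 | 20.4% |
| 30% / 10% | +0.5 / 0 | −0.15 | 37.1% |

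A simulation of 40,000 trials with a t test gave 9.0% and 8.7% for the first two rows, and 5.0% for equal exclusion with equal gaps.

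**5. Power under bias**

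True effect 0.245, 15% against 5% excluded:

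- no bias: 0.245/0.0862 = 2.84, power 81%;
- bias against the app: 0.195/0.0862 = 2.26, power 62%;
- bias toward the app: 0.295/0.0862 = 3.42, power 93%.

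**6. Power from the loss of numbers alone**

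The plan does not say whether 300 per arm is randomised or evaluable.

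| Excluded | Analysed per arm, if 300 are randomised | Power at 0.245 | Randomised per arm to keep 300: 300/(1 − share) |
|---|---|---|---|
| 10% | 270 | 81.1% | 334 |
| 20% | 240 | 76.4% | 375 |
| 30% | 210 | 70.7% | 429 |

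**The case against.** The best defence is that the sentence naturally describes people who did neither thing. Nobody with a primary outcome would then be lost, and the trial would have an ordinary available-case analysis of a self-reported endpoint. The design also limits differential loss: participants and statisticians were masked, both apps share an interface, and familiarisation, weekly reminders and telephone calls are described without distinction by arm. No document gives an exclusion rate or an outcome gap, so the bias is hypothetical, and in the milder scenarios it is only 0.03 to 0.05 SD. The largest figures need selection in the app arm alone.

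Much of this is fair. The text does not settle which reading applies, the safeguards do reduce the risk, and no bias has been shown. But the milder reading still leaves missing opioid outcomes with no analysis. Masking does not make educational and data-only content equally engaging, and telephone follow-up is data collection, not an analysis of those who remain missing.

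Four narrower points also stand:

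- Delta-adjusted imputation is only one acceptable method, and on a log scale it first needs a rule for zero opioid use, which the documents do not give.
- The text is in the past tense, so enlarging the sample may no longer be possible.
- By-arm exclusions may already appear in the trial's CONSORT reporting.
- The timing of the re-hospitalization exclusion is a side question. An event can be both an exclusion and a recorded safety event, and the main point does not depend on it.

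**Conclusion.** The concern holds. The primary analysis set is defined by behaviour after randomisation, engagement is undefined, and no planned analysis would show whether the result depends on the exclusions. Confidence is high that this gap exists. The direction and size of any bias cannot be determined from the documents.

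Under the assumed rates and gaps, the bias runs from zero (equal rates, equal gaps) through 0.05 SD to 0.15 SD, or 61% of the design effect, when 30% are lost in the app arm and selection occurs only there. Equal exclusion rates alone are not protective. The documents give no SD for log opioid use, so these shifts cannot be restated as ratios of geometric means. The power loss applies only if the 300 per arm are randomised participants.

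Because this affects the primary estimate and can be remedied with existing data, it should be corrected before the primary result is relied on.

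**What to change.** 1. Remove non-engagement as a ground for exclusion from the primary analysis.
2. Analyse every participant with a four-week opioid outcome, from app or telephone, in the arm to which they were randomised.
3. Tabulate exclusions and missing outcomes by arm with reasons, or point to where this is already reported. State whether 300 per arm means randomised or evaluable.
4. Add one sensitivity analysis for missing four-week opioid use. One option is multiple imputation by arm using surgical subspecialty, pre-operative opioid use, in-hospital opioid intake and discharge pain score, with a delta shift varied separately by arm in both directions. State first how zero use is handled on the log scale.
5. Keep the engaged set, if wanted, as a labelled supplementary analysis, with engagement defined by a criterion that both arms can meet.
6. State when the re-hospitalization exclusion applies and reconcile it with the serious adverse event definition, so that events after randomisation are not lost from the randomised set or from safety reporting.

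The cost is revised wording in the analysis and eligibility sections, one table and one imputation program, with no new data collection. The estimate may be diluted by people who never used the app, but that is part of the effect of being assigned to it.

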The primary outcome was self-reported cumulative oral morphine milligram equivalents (MME) in the first four weeks after discharge. The secondary outcomes were amount of opioid prescription at discharge, supplementary opioid prescriptions within four weeks after discharge, disposal of leftover opioids within four weeks of discharge, pain intensity scores during the four weeks after discharge, and pain interference scores during the four weeks after discharge. Non-opioid prescriptions within four weeks of discharge were an exploratory outcome. Pain intensity and interference were both quantified using the National Institutes of Health Patient-Reported Outcomes Measurement Information System (PROMIS®) four-item pain intensity scale at four weeks and the four-item scale pain interference score at four weeks. All PROMIS™ scores were analyzed as standardized T-scores (mean 50, standard deviation 10).

Independent variables included sociodemographic characteristics obtained from the electronic health record and from a questionnaire provided to participants during their hospitalization: age, sex, race, ethnicity, body mass index (kg m²-1), and insurance type. Health history variables were obtained via surveys and electronic health records as necessary and included history of substance use disorder, PROMIS™ Sleep Disturbance Score, Patient Health Questionnaire-(PHQ-8) score, pre-operative opioid use, preoperative benzodiazepine use, preoperative gabapentinoid use, and preoperative antidepressant use. Clinical characteristics included the primary surgical subspecialty for the requisite hospital stay, multiple procedures performed during admission, total in-hospital opioid intake, pain score at discharge, and length of hospital stay.

Adverse events were monitored. For this study, an adverse event was considered as one requiring more than two additional opioid prescriptions within two weeks of discharge and/or access of confidential information by a non-authorized person. We considered a serious adverse event as all-cause mortality and/or re-hospitalization for any reason.

Statistical analysis

Baseline balance on potential confounding characteristics was assessed using absolute standardized difference (ASD), calculated as the difference in means or proportions divided by the pooled standard deviation. A variable was considered imbalanced if the ASD was greater than 0.16.

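### Missing pain scores are said to be imputed from the mixed model that tests the app; done as one fill-in and refit, this makes the standard errors of the two secondary pain outcomes too small

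*Combined protocol and SAP*

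**What the plan says.** The paragraph on the primary analysis in the Statistical analysis section closes with the handling of missing data. For opioid outcomes it reports "There were no partial responses to the opioid-related outcomes". For pain it says "Missing data from pain-related survey responses were imputed from the mixed effects model". The analysis set is modified intention-to-treat, "excluding participants that did not engage with the intervention or answer survey questions".

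The next paragraph, on the secondary analysis, gives the only mixed model in the documents: "The effect of the app on pain intensity and interference t-scores was evaluated by fitting linear mixed models". Its fixed effects are app group and categorical time, and it has "random effects for participant identification code".

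The Outcomes section lists both pain measures among five secondary outcomes: "pain intensity scores during the four weeks after discharge, and pain interference scores during the four weeks after discharge". The Procedures section describes a weekly notification to participants, "reminding them to complete standardized surveys and custom questionnaires during the first four weeks following discharge", with telephone follow-up when the app brought no response.

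Not stated: whether imputation was single or multiple, whether residual error was added to the predictions, whether imputed values went back into the analysed data, and how imputation uncertainty entered the standard errors. Nor do the documents give the amount of missing pain data, the missing-data assumption, or a sensitivity analysis for missing pain scores.

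**The concern.** Read at face value, the imputation sentence points to the model that contains the app effect under test. If a missing score is replaced by that model's prediction and the model is fitted again, two things go wrong. The filled-in score carries no residual variation, so the within-person variance is estimated too low. The refit also counts more observations than were made. Both shrink the standard error of the app effect.

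Nothing is gained in exchange. A mixed model fitted to incomplete data already uses every observed weekly score and is valid under missing at random. A prediction from the same model brings no new information.

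At stake are the intervals and p-values for pain intensity and pain interference. Intervals that are too narrow can suggest a pain benefit or harm that is not there, or wrongly rule one out. That matters for an app meant to reduce opioid intake, where readers will ask whether pain control was kept.

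**Working it through.** **Inputs from the documents.** 300 per app group, two-sided alpha 0.05, 85% power and effect size 0.244 for week-one pain intensity (Sample Size Justification); T-score SD 10 (Outcomes); app group, categorical time and a participant random effect (Statistical analysis), taken as a random intercept. Four weekly scores is my reading of the weekly survey prompts (Procedures).

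**Assumed, because the documents are silent.** Within-person correlation ρ of 0.3, 0.5 or 0.7; 10% to 40% of scores missing completely at random; no true app effect.

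**1. The plan's own figure.** Power = Φ(0.244 × √(300/2) − 1.96) = Φ(2.988 − 1.960) = Φ(1.028) = 84.8% (84.7% with the t distribution). The stated 85% for pain intensity reproduces and is not in dispute.

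**2. What one fill-in discards.** Write λ = ρ/(1 − ρ). For a participant with m observed scores, the participant-specific prediction is the fixed part plus λ/(1 + mλ) times the sum of that participant's residuals. Around it, the true missing score has variance σ²ₑ + σ²ᵤ/(1 + mλ). With ρ = 0.5, σ²ₑ = σ²ᵤ = 50 and λ = 1. With m = 3 the variance is 50 + 50/4 = 62.5, an SD of 7.9 T-score points. A single fill-in treats this as zero.

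**3. Effect on the test.** 1,000 simulated trials per setting, with REML fits. Each entry is the average SE after fill-in and refit, divided by the average SE of the mixed model on observed scores; the simulated type I error at nominal 5% is in brackets (simulation error about 0.7 points).

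| Missing | ρ = 0.3 | ρ = 0.5 | ρ = 0.7 |
|---|---|---|---|
| 10% | 0.953 (5.9%) | 0.972 (5.9%) | 0.986 (4.5%) |
| 20% | 0.900 (7.7%) | 0.939 (6.9%) | 0.968 (4.9%) |
| 30% | 0.843 (9.6%) | 0.901 (6.8%) | 0.946 (7.4%) |
| 40% | 0.783 (12.2%) | 0.860 (9.4%) | 0.922 (5.9%) |

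The shortfall is one minus the ratio: 1.4–4.7% at 10% missing, 3.2–10.0% at 20%, 5.4–15.7% at 30%.

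**4. Check by formula.** If the estimate keeps its spread and only the SE shrinks by a ratio r, type I error is 2Φ(−1.96r). For r = 0.843 this is 9.8%, and for r = 0.783 it is 12.5%, in line with the table.

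**5. A second simulation.** 1,500 trials per scenario with ρ = 0.5 gave SEs, in SD units, of 0.0637/0.0655 = 0.97, 0.0626/0.0667 = 0.94 and 0.0616/0.0683 = 0.90 at 10%, 20% and 30% missing. With ρ = 0.3 and 30% missing it gave 0.0518/0.0616 = 0.84. These SE ratios agree with the table. Its type I error for that last setting was about 12%, above the 9.6% in the table and the 9.9% that its own ratio implies. I therefore take about 10–12% for that setting.

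**6. The alternative.** The mixed model on observed scores alone had type I error of 3.8–5.8% and an average SE of 0.96–1.04 times the true SD of the estimate. After participant-specific fill-in, the SD of the estimate was the same in every setting (for example 0.595 in both at ρ = 0.3 and 30% missing). So the fill-in changed only the reported SE.

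**The case against.** A reader might infer that the trial did analyse predicted values as data and that its pain standard errors are therefore wrong. The documents do not support that. They never say that imputation was single or deterministic, or that completed data were refitted. The sentence sits beside the analysis-set statement, before the pain model is introduced, so it may be a general remark and not a sequence of steps. It could be shorthand for letting the mixed model handle missing weeks by likelihood, or it could mean multiple imputation from that model. Neither has this fault.

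The size is also open. With 10% missing and participant-specific predictions the distortion is small. Telephone follow-up and the exclusion of people who answered no surveys may both hold down missingness in the analysed set, though neither proves that it was low.

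A reader might also reach for harsher scenarios. Filling with fixed-effect means only gives SE ratios of 0.71–0.73 at 30% missing and type I error up to 22.2% across 10–40% missing, but nothing in the documents says that this kind of prediction was used. Weekly dropout of 15–20% gave an SE 8–11% too small. If dropout starts after week one, it means 1 − 0.85³ = 39% to 1 − 0.80³ = 49% missing by week four, which the documents do not support, and those runs were not repeated. The conclusion rests on neither.

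These points make the finding conditional; they do not remove it. Likelihood fitting imputes nothing, so on that reading the sentence describes a step that did not take place. Multiple imputation needs combining rules, which are absent. The sentence needs correcting on every reading.

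**Conclusion.** The point holds in conditional form. The plan names an imputation step from the model under test and nothing that would carry the imputation uncertainty into the standard errors. If that step is one participant-specific fill-in followed by a refit, the standard errors of the two secondary pain outcomes are too small by about 1–5%, 3–10% and 5–16% at 10%, 20% and 30% missing. Type I error reaches about 12% in the worst settings (low correlation with 30–40% missing) and stays close to 5% when little is missing. These figures rest on 300 per arm, four weekly scores, a random intercept, correlation of 0.3 to 0.7 and scores missing completely at random.

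Under likelihood-based handling, or multiple imputation with proper combining, the pain results stand as they are. The primary opioid outcome is untouched on any reading: it has its own linear regression, and the imputation sentence covers pain responses only. The correction should be made, but it does not threaten the main conclusion.

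**What to change.** Replace the imputation sentence with: *Linear mixed models are fitted by REML to all observed weekly pain scores under missing at random, with no fill-in of missing scores.* State what was actually done, and report the number of missing pain scores by arm and week so that the size of the issue can be judged.

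If completed data are wanted for a check under missing not at random, use multiple imputation, state the imputation model and the number of imputations, and combine the results with Rubin's rules.

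Cost: one sentence and a short table. If scores were filled in once, the two pain models must also be refitted, and their intervals become slightly wider. If they were not, no result changes.
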